### 2.2. Subgroups Definitions

To explore the impact of the baseline status:

Subgroups of subjects with PPFEV1  $< 90$  and  $\geq 90\%$  at baseline will be considered for PPFEV1 and CFQ-R RSS endpoints analyses.

Subgroups of subjects with CFQ-R RSS  $< 75$  and  $\geq 75$  at baseline will be considered for CFQ-R RSS endpoints analyses.

The following subgroups of CFQ-R RSS at baseline by range of 10 points will also be considered for CFQ-R RSS analyses: ..., [50;60[, [60;70[, [70;80[, [80;90[, [90;100].

## 3. ANALYSES

### 3.1. ppFEV1 (%)

Descriptive summaries will be performed on Per Protocol Populations and Sensitivity Population excluding outliers of PPFEV1. Summaries will be repeated on subgroups of PPFEV1 at baseline for the 3 populations.

The mixed-model analysis described in the SAP will be repeated on the Per Protocol and Sensitivity Populations (using the following time points: Baseline, Day 4, Day 5 pre-dose, Day 8 pre-dose, Day 15 pre-dose, Day 22 pre-dose, Day 26 pre-dose, Day 26 4 hours post-dose, Day 33 and Day 54. Differences versus Placebo will be estimated at Day 15, Day 26 pre-dose, Day 26 4 hours post-dose, Day 33 and Day 54). Differences versus Placebo at Day 15 will also be assessed on Exploratory Population (in addition to planned time points).

The mixed model analysis will also be carried out on subgroups of PPFEV1 at baseline for the 3 populations. Due to the small sample size, the following time points only will be included in the model: Day 15 pre-dose, Day 26 pre-dose and Day 33.

The sensitivity analysis including presence/absence of *Pseudomonas aeruginosa* at Baseline as a covariate will be repeated on Per Protocol Populations. Day 15 will be added as time point of interest for both Exploratory and Per Protocol Populations.

Analyses to explore the dose response using the MCPMOD methodology as described in the SAP will be followed and repeated on Per Protocol Populations. The change from baseline in ppFEV1 at Day 15 pre-dose (also on Exploratory Population), Day 26 pre-dose, Day 26 4 hours post-dose, Day 33 and Day 54 will be assessed.

In addition to the dose-responses shapes described in the SAP, a quadratic model with umbrella-shape will be tested. Parameters of the dose-responses shapes models may be adapted to fit the data.

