13.12 Subgroup Analyses

No subgroup analyses are planned.

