## 2.4. Randomization Methodology

Within each dosing cohort, subjects will be randomized 3:1, QR-010 to placebo.

The randomization is performed using a centralized interactive web response system (IWRS).

Study drug will be administered in a double-blind fashion. Study drug and placebo are both clear, colorless, and odorless aqueous solutions. Subjects, Investigators and study site staff will be blinded to treatment assignment. However, due to the requirement for study pharmacist(s) to prepare the various study drug dilutions depending on the dosing cohort to which a given study subject is assigned, the study pharmacist(s) will be unblinded to treatment assignment.

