## **4. STATISTICAL METHODS**

### **4.1. Sample Size Justification**

This is a Phase 1 safety study designed to evaluate the safety, tolerability and PK of QR-010. The sample size is not based on power calculations. It is chosen based on clinical experience and considered to be adequate to fulfill the objectives of the study.

Approximately 64 subjects will be enrolled in the study, with 8 subjects per cohort (6 QR-010 and 2 placebo), 32 each in the SAD and MAD portions of the study. The exact number of subjects enrolled is dependent on whether any dose levels are to be expanded due to the occurrence of AEs of interest.

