**Table 4: Header for the MAD Cohort**

	Placebo	QR-010 6.25 mg	QR-010 12.5 mg	QR-010 25 mg	QR-010 50 mg	Total MAD (optional)
Screened	...	...	...	...	...	...
Screen failure						
Treated						
Exploratory Analysis Population						
Safety Population						
xxx						

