### **3.2. CFQ-R (Cystic Fibrosis Questionnaire – Revised) RSS**

Descriptive summaries will be repeated on Per Protocol Populations. Summaries will be repeated on subgroups of PPFEV1 at baseline (<90; >=90) and CFQ-R RSS at baseline (<75; >=75 and subgroups by 10 points).

The mixed model analysis on CFQ-R RSS score described in the SAP will be repeated on Per Protocol Populations. Differences versus placebo will be estimated at Day 15, Day 33 and Day 54.

The mixed model analysis will be performed on subgroups of PPFEV1 at baseline (>90; >=90) and CFQ-R RSS at baseline (<75; >=75) for the 2 populations.

Dose-response analyses using MCPMOD methodology will be repeated on the Per Protocol Population. Thresholds of +4, +5, +8 and +10 +12 will be tested as sizes of interest of treatment effect.

In addition to the dose-responses shapes described in the SAP, a quadratic model with umbrella-shape will be tested. Parameters of the dose-responses shapes models may be adapted to fit the data.

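### The post hoc addendum fits separate mixed models within baseline subgroups of the MAD portion and never estimates whether the treatment effect depends on baseline

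*SAP*

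**What the plan says.** Section 2.2 of the post hoc addendum gives the purpose of the subgroups: "To explore the impact of the baseline status". It defines baseline ppFEV1 below 90 versus 90 or more, and baseline CFQ-R RSS below 75 versus 75 or more. Ten-point CFQ-R RSS bands are also defined, but addendum 3.2 uses them only for descriptive summaries.

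Addendum 3.1 then says "The mixed model analysis will also be carried out on subgroups of PPFEV1 at baseline for the 3 populations", with the visits cut to Day 15 pre-dose, Day 26 pre-dose and Day 33 because of the small sample. Addendum 3.2 says "The mixed model analysis will be performed on subgroups of PPFEV1 at baseline" and by the CFQ-R RSS cut, in two populations.

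The models come from main SAP 4.8.2.1 and 4.8.2.9: treatment, baseline value of the outcome, time, and time-by-treatment, with unstructured covariance by default. SAP 4.2.6 sets two-sided 5% (or one-sided 2.5%) with no multiplicity adjustment. Protocol 13.12 says "No subgroup analyses are planned".

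On size, SAP 4.1 plans cohorts "with 8 subjects per cohort (6 QR-010 and 2 placebo), 32 each in the SAD and MAD portions of the study" and adds "The sample size is not based on power calculations".

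**The concern.** Whether a treatment effect depends on baseline is a question about the difference between two subgroup effects. Fitting the same model twice, once per subgroup, gives two effects and no estimate of their difference. A reader is left to compare the two results by eye, usually by which one reaches significance. That comparison is unreliable even when the effect is identical in both groups, and more so when each group holds only a few subjects per arm.

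What is at stake is the design of the next trial. Protocol 4.1.3 says that observed changes in FEV1 and CFQ-R RSS may inform future studies, so a chance contrast between subgroups could shape the next target population. No primary, secondary or safety conclusion of this study depends on these fits.

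**Working it through.** **Inputs.** SAP 2.4: "Within each dosing cohort, subjects will be randomized 3:1, QR-010 to placebo". SAP 4.1 gives 8 per cohort. SAP Table 4 ("Header for the MAD Cohort") has one placebo column and four dose columns. The documents give no subgroup split, SD or target power, so those below are assumptions and results are in SD units.

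**The plan's own figures.** 8 cohorts × 8 = 64; 4 MAD cohorts × 8 = 32. Pooled placebo is 4 × 2 = 8, with 6 per dose. If every cohort gains 4 subjects (Protocol 5.2, about 96 in total), MAD reaches 4 × 12 = 48.

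**Discordant significance.** The subgroups contain different subjects and are fitted separately, so independence is assumed. With power p in each, the chance that exactly one is significant is 2p(1 − p).

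| Situation | p | 2p(1 − p) |
|---|---|---|
| No effect | 0.05 | 9.5% |
| Same effect in both | 0.10 | 18% |
| Same effect in both | 0.30 | 42% |
| Same effect in both | 0.50 | 50% (maximum) |

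As one anchored case, take a uniform effect large enough for 80% power in all 32 subjects (1.57 SD). At a 50/50 split, power per subgroup is 46%, and 2 × 0.46 × 0.54 = 50%.

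These figures are per pair of comparisons. A simulation with no effect, 4 doses and 3 visits (no covariate, 50/50 split, assumed within-subject correlation 0.7) gave a 53% chance that at least one comparison is significant in exactly one subgroup (44% to 58% for correlation 0.9 to 0.5).

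**Precision at an assumed 50/50 split** (4 placebo, 3 per dose in each subgroup). These are single-visit approximations. SE = √(1/n_placebo + 1/n_dose). Residual df are n − 6 for one fit (five arms plus baseline) and 32 − 11 for a joint fit (ten cells plus baseline).

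| Analysis | SE | df | t(0.975) | 95% half-width |
|---|---|---|---|---|
| All 32 | √(1/8 + 1/6) = 0.540 | 26 | 2.056 | 1.11 SD |
| Subgroup, separate fit | √(1/4 + 1/3) = 0.764 | 10 | 2.228 | 1.70 SD |
| Subgroup, joint fit | 0.764 | 21 | 2.080 | 1.59 SD |

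The cost of fitting separately is 2.228 / 2.080 = 1.07, or 7% wider. The larger loss, 0.764 / 0.540 = 1.41, comes from subgrouping and is the same in either fit. With an assumed 22/10 split the smaller group has 10 − 6 = 4 df and t = 2.776, so its interval is 2.776 / 2.080 = 1.33 times the joint one. At 8/24 it has 2 df and t = 4.30, about 2.07 times.

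**Sparse cells.** If each subject falls in either half with probability 0.5, the chance that some arm has no subject in a subgroup is 1 − (1 − 2/64)⁴(1 − 2/256) = 13%. The chance that some arm has 0 or 1 is 1 − (1 − 14/64)⁴(1 − 18/256) = 65%.

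**What an interaction can deliver.** The contrast between the two subgroup effects has SE √2 × 0.764 = 1.08 SD, twice the overall 0.54. If the 1.57 SD effect exists in one half only, the two-sided 5% interaction test on 21 df has about 28% power.

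**The case against.** The strongest reply is that this work is openly exploratory. The addendum calls itself post hoc. Protocol 13.4 treats any inferential statistics as hypothesis generation, Protocol 13.1 has unplanned analyses identified as such in the CSR, and Protocol 4.1.3 says the study is not powered for efficacy. The parent model reports adjusted means with intervals, and the subgroup models are already trimmed to three visits. A weakly powered interaction test adds little, and a joint model leaves most of the imprecision and the sparse cells in place.

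Much of this stands. It confines the issue to interpretation rather than a confirmatory error rate, and it rules out using the interaction test as a gate on describing anything. It does not supply the missing estimate: labelling an analysis exploratory does not tell a reader whether two subgroup effects differ. A wide interval for the difference would show how little these data can say.

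Several stronger readings are tempting and should be resisted:

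- A reader might infer that the sponsor plans a subgroup-only claim. No section says so.
- A reader might infer a breach of Protocol 13.12. Protocol 13.1 allows disclosed unplanned analyses.
- A reader might infer that the model has no interaction at all. It has time-by-treatment; what is missing is treatment-by-baseline.
- A reader might infer that every fit dichotomises a covariate it already contains. The CFQ-R RSS model carries baseline CFQ-R RSS, not baseline ppFEV1, and nothing says the continuous covariate is dropped.
- A reader might multiply 3 × 2 × 4 × 3 = 72 ppFEV1 and 2 × 4 × 4 × 3 = 96 CFQ-R contrasts into 168. The populations are nested, addendum 3.1 does not list the contrast visits for its subgroup models, and subgroup contrasts would remain under a joint model. The point does not rest on that count.

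**Conclusion.** The point holds as an analysis that does not answer its own question. Addendum 2.2 does not spell out that the interest is in baseline status modifying the treatment effect, but that is its natural meaning, and sections 3.1 and 3.2 contain no quantity that measures it. Comparing separate p-values cannot stand in: discordance is 9.5% per pair with no effect and 18% to 50% with a uniform effect. That range rests on an assumed 10% to 50% power per subgroup and on independence. It does not make a discordant result more likely than not for a single pair.

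The precision cost of separate fitting is modest at an even split (about 7%) and grows as one subgroup shrinks; the rest of the loss belongs to subgrouping itself. All precision figures use the planned 32. MAD could grow to about 48, while the Per Protocol and Sensitivity sets cannot exceed the exploratory set. This is a worthwhile, inexpensive improvement to an exploratory analysis.

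**What to change.** For each population and each baseline variable, replace the paired subgroup fits by one model on all subjects. Add treatment × continuous baseline and its interaction with time; for CFQ-R RSS by lung function, this means bringing baseline ppFEV1 into the model. Pool doses if the data are too sparse for dose-specific slopes. Report the interaction estimate with its 95% CI, and take any effects at low or high baseline from that model. Descriptive summaries by subgroup can stay. Add two sentences: that a difference between subgroups will not be inferred from separate p-values, and that the interaction estimate is exploratory. While editing, correct the ppFEV1 cut in addendum 3.2, where the mixed-model sentence prints >90 and >=90 although 2.2 defines <90 and >=90.

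The cost is addendum wording and a model statement, with no new data. Fits fall from 3 × 2 + 2 × 4 = 14 to 3 + 2 × 2 = 7. The downsides should be disclosed: a common covariance and linear baseline slopes are assumed, the latter with about 6 subjects per dose. Power for the interaction is low (about 28% in the 50/50 categorical scenario; the continuous version was not calculated), so a non-significant interaction must not be read as evidence of a uniform effect.

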### **3.2. CFQ-R (Cystic Fibrosis Questionnaire – Revised) RSS**

Descriptive summaries will be repeated on Per Protocol Populations. Summaries will be repeated on subgroups of PPFEV1 at baseline (<90; >=90) and CFQ-R RSS at baseline (<75; >=75 and subgroups by 10 points).

The mixed model analysis on CFQ-R RSS score described in the SAP will be repeated on Per Protocol Populations. Differences versus placebo will be estimated at Day 15, Day 33 and Day 54.

The mixed model analysis will be performed on subgroups of PPFEV1 at baseline (>90; >=90) and CFQ-R RSS at baseline (<75; >=75) for the 2 populations.

Dose-response analyses using MCPMOD methodology will be repeated on the Per Protocol Population. Thresholds of +4, +5, +8 and +10 +12 will be tested as sizes of interest of treatment effect.

In addition to the dose-responses shapes described in the SAP, a quadratic model with umbrella-shape will be tested. Parameters of the dose-responses shapes models may be adapted to fit the data.

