#### Cystic Fibrosis Questionnaire- Revised Respiratory Symptoms Score (CFQ-R RSS)

The CFQ-R RSS is calculated based on mean score of Questions 40 to 46 excluding question 43 as below if  $\leq 3$  item scores are missing:

Assuming a coding of 1 to 4 with categories such as

1=A great deal / Always

2=Somewhat / Often

3=A little / Sometimes

4=Not at all / Never,

$$\text{CFQ-R RSS} = \text{mean} [(\text{resp40}, \text{resp41}, \text{resp42}, \text{resp44}, \text{resp45}, \text{resp46})-1]/3*100;$$

The score will be missing if more than three of the six scores are missing.

Descriptive summary overtime will be provided for the values and change from baseline at each time point following the time windows, by treatment group.

A mixed model analysis with repeated time measures on the change from baseline of CFQ-R RSS as outcome variable, including treatment, baseline CFQ-R RSS value, time and interaction between time and treatment as covariates will be performed. By default, an unstructured covariance matrix will be used, unless convergence issue occurs, in which case other covariance matrix will be explored. Adjusted means and corresponding confidence interval will be presented. The following time points will be included in the repeated measures analysis: Baseline, Day 15, Day 33 and Day 54. Differences versus placebo will be estimated at Day 33 and Day 54.

A dose-response analysis using MCPMOD methodology will be performed with change from baseline of CFQ-R RSS at Day 33 as dependent variable, the treatment (0, 6.25, 12.5, 25, 50 mg) and CFQ-R RSS at baseline as factors. Thresholds of +4, +5, +8 and +10 will be tested as sizes of interest of treatment effect.

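### SAP addendum 3.2 gives overlapping ppFEV1 subgroups (>90 and ≥90) for the CFQ-R RSS mixed model, so as written no separate model is fitted below 90%

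*SAP*

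**What the plan says.** The addendum that follows SAP V1.0 sets out post hoc analyses for the MAD part. It states the baseline ppFEV1 split in three places that bear on CFQ-R RSS.

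- **Addendum 2.2 (Subgroups Definitions)** names two groups, baseline ppFEV1 below 90 and 90 or above. It gives their scope: these groups "at baseline will be considered for PPFEV1 and CFQ-R RSS endpoints analyses".
- **Addendum 3.2, descriptive paragraph**, uses the same pair: "Summaries will be repeated on subgroups of PPFEV1 at baseline (<90; >=90".
- **Addendum 3.2, mixed-model sentence**, prints a different pair: "The mixed model analysis will be performed on subgroups of PPFEV1 at baseline (>90; >=90". The sentence goes on to a second split, "CFQ-R RSS at baseline (<75; >=75) for the 2 populations".

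The CFQ-R RSS mixed model is also run without any ppFEV1 restriction. SAP section 4.8.2.9 specifies it as "A mixed model analysis with repeated time measures on the change from baseline of CFQ-R RSS as outcome variable", and SAP section 4.8 places efficacy analyses on the exploratory analysis population. Addendum 3.2 adds that "The mixed model analysis on CFQ-R RSS score described in the SAP will be repeated on Per Protocol Populations".

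**The concern.** The printed pair is not a split. Both groups sit at the upper end, one inside the other, and neither contains a subject below 90. The sentence sets the data filter for a model that yields placebo-referenced estimates, so it is an instruction to the programmer and not background text.

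If it is followed as printed, the CFQ-R RSS mixed model has no separate fit for subjects with lower lung function at baseline, and the fit at 90 and above is produced twice. The addendum's purpose in 2.2 is to look at the effect of baseline status. A comparison of modelled treatment effects across the ppFEV1 cut-point would then be unavailable for CFQ-R RSS. The stratum below 90 can be populated: protocol section 5.3, inclusion criterion 12, admits subjects from 70% predicted at screening.

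**Working it through.** There is no planned figure to reproduce. The check is set logic on the cut-points, followed by a count of the affected fits.

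**1. The cut-points side by side**

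| Place | First group | Second group | Disjoint? | Covers everyone? |
|---|---|---|---|---|
| Addendum 2.2 | <90 | ≥90 | Yes | Yes |
| Addendum 3.2, descriptive | <90 | ≥90 | Yes | Yes |
| Addendum 3.2, mixed model | >90 | ≥90 | No | No |

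**2. The printed pair.** Let x be baseline ppFEV1. The set {x > 90} is contained in {x ≥ 90}. Their union is {x ≥ 90}, and they differ only at x = 90. SAP section 4.5 computes ppFEV1 as a ratio of measured to predicted FEV1, so unless values are rounded an exact 90 is unlikely and the two sets would usually be the same subjects. No subject with x < 90 is in either.

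**3. Fits affected.** Addendum 2.2 lists the ppFEV1 and CFQ-R RSS splits separately, so I read them as separate and not crossed. I take the two populations to be Exploratory and Per Protocol. The intended subgroup fits are then (2 ppFEV1 groups + 2 CFQ-R RSS groups) × 2 populations = 8. As printed, 1 × 2 = 2 of these (the <90 fit in each population) are replaced by near-duplicates of the ≥90 fit.

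**4. Contrasts affected.** The subgroup sentence names no contrast days, so the documents fix no count. With four doses against placebo:

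- Using the Per Protocol days in addendum 3.2 (15, 33, 54) for Per Protocol, and the main SAP days (33, 54) for Exploratory: 3 × 4 + 2 × 4 = 20.
- Using Days 15, 33 and 54 in both populations: 3 × 4 × 2 = 24.

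These counts are conditional. Addendum 3.1 shortens the time-point list for the ppFEV1-endpoint subgroup model because of sample size, and the same might be done here.

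**5. Where subjects below 90 still appear**

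- The main SAP CFQ-R RSS mixed model, on the whole exploratory population.
- Its Per Protocol repeat, for those with at least 10 of 12 doses (addendum 2.1).
- The CFQ-R RSS <75 and ≥75 subgroup models.
- The ppFEV1-endpoint subgroup model in addendum 3.1, which restates no cut-points and so takes them from 2.2.
- The CFQ-R RSS descriptive summaries by ppFEV1 <90 and ≥90.

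**6. With the correction.** Using <90 and ≥90, every subject with a baseline ppFEV1 falls in exactly one group, and both groups are modelled.

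**The case against.** The strongest answer is that this is a slip of one character which the addendum itself resolves. Section 2.2 is the definitions section, it covers CFQ-R RSS expressly, and nothing competes with it. The descriptive paragraph of 3.2 agrees with it, and the neighbouring CFQ-R RSS pair in the same sentence is correctly formed. Nobody would choose >90 against ≥90 on purpose, and two outputs with almost the same subject numbers would be noticed at review.

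The point about intent stands, and it makes the remedy certain. It does not make the sentence correct. Section 3.1 leaves its cut-points to 2.2, whereas 3.2 prints its own, and no rule says which governs. A programmer who quietly used 2.2 would be making an undocumented choice in a post hoc analysis.

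It is also fair to say that little information is at stake. The MAD part plans 8 subjects in each of four cohorts, 6 active and 2 placebo. At most 6 subjects per dose and 4 × 2 = 8 placebo subjects are therefore divided between the two ppFEV1 groups. Estimates from either group would be imprecise, so the number of missing contrasts is not a measure of information lost.

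**Conclusion.** The inconsistency is real, and the mixed-model sentence is wrong as printed. Taken literally, it drops one CFQ-R RSS subgroup fit (<90) in each of two populations and duplicates the other.

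Two stronger readings are tempting, and the documents support neither. A reader might infer that subjects below 90% are never modelled for CFQ-R RSS. That is not so: they remain in the unrestricted mixed models (subject to the dose rule for Per Protocol) and in the CFQ-R RSS subgroup models. A reader might also infer that CFQ-R RSS cannot be examined by baseline ppFEV1 at all. That is too broad, because the descriptive summaries by <90 and ≥90 are planned, and addendum 3.3 correlates the two measures. Nor can a number of affected subjects be derived, since the documents give no baseline distribution of ppFEV1.

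The point is minor. The analysis is post hoc and exploratory, in a study whose sample size was not based on power (SAP section 4.1), and no primary, safety or MTD conclusion depends on it. This rests on reading the two splits as separate and the two populations as Exploratory and Per Protocol.

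**What to change.** In the mixed-model sentence of addendum 3.2, replace (>90; >=90) with (<90; >=90), or drop the cut-points and refer to section 2.2. Confirm the character against the signed addendum, and check that the program filter for this model matches 2.2. If the model has already been run on the printed pair, fit the <90 model and withdraw the duplicate output. The cost is one character and one filter check. No new data are needed and no other analysis changes.
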